The hardware (device) is minimal risk and has been used on a variety of studies. All sensors (esophageal catheter, RIP, and spirometry) have appropriate clearance through FDA approval or 510K equivalence for use in children, and have been used in our previous investigations. The two pieces of the software (tool to help interpret raw signals from the sensors), and the CDS ventilator management protocol have both previously been deemed non-significant risk because they are primarily implemented in an open-loop application, incorporate current evidence based guidelines (computer CDS protocol), or have been iteratively tested against FDA approved post-processing programs as part of our previous investigations. Moreover, clinicians are free to reject protocol recommendations, and to that end this data is to be used simply as an adjunct to clinical assessment, rather than a replacement.

E2 Subject Recruitment Plans and Consent Process

The subjects of this study are critically ill infants and children who will not be able to consent for their own participation in this study. One or both parents will be informed about the study and given an opportunity to voluntarily give their consent/permission for their child to participate. Assent of child subjects will not be possible because they are critically ill, intubated on a ventilator, and sedated. Thus, assent will be waived. Families or guardians of any intubated and mechanically ventilated child who meet inclusion and do not meet exclusion criteria will be approached for consent. Consent will be attained by the study investigator, co-investigator, or research nurse. Consent will be documented on a consent form, and stored in a study binder, identified by patient number. This binder will be stored in a locked cabinet in the office of the site principal investigator.

E3 Risks and Benefits

E.3.1 Risks:

1. Placement of the esophageal catheter. While this procedure is very well tolerated, there is a very small risk for bleeding, incorrect placement into the lungs or other body cavities, or damage to the esophagus, stomach, or nasal or oral mucosa. Patients at high risk of bleeding (thrombocytopenia, coagulopathy, mucositis), will not be included in the study.
2. Small amount of discomfort when placing the esophageal catheter, although nearly all patients will be receiving analgesia and sedation as part of mechanical ventilation. Intermittent doses of already prescribed sedative or analgesia medications may be administered to minimize pain during placement.
3. A particular computer generated recommendation may not be correct for the patient at that time, and the clinicians may choose not to follow them.
4. There is potential of accidental release of confidential information.
5. There is a possibility of transient fall in oxygen levels during airway occlusion maneuvers, although patients will be pre-oxygenated as per ICU standard practices prior to measurement, and patients must pass the oxygenation test prior to performing these measurements.

E.3.2 Potential Benefits to Subjects

There is the prospect of direct benefit to subjects in both arms. For the intervention arm, using the intervention tool has the potential to significantly shorten length of assisted breathing, lower re-intubation rates, increase Ventilator Free Days (VFDs), shorten ICU and hospital length of stay, and reduce exposure to sedatives and analgesics. Patients in the control arm also have potential to benefit as enrollment in the study will prompt more consistent use of evidence based weaning guidelines including a daily Spontaneous Breathing Trial. This may also result in more days free of ventilators compared to those not enrolled in the study.

E.3.4 Importance of the Knowledge to Be Gained

Completion of this study will elucidate important information on the pathogenesis and timing of respiratory muscle weakness during MV in children, and whether this weakness can be mitigated by promoting more normal patient effort during MV. These data can lead to immediate change in practice by implementing mechanical ventilation strategies that promote more patient effort of breathing. They will also form the basis to determine whether a larger, Phase III multi-center study of REDvent is indicated, which would focus on key clinical outcomes such as 28-day Ventilator Free Days. Given that the risks to the study participants are small, the information gathered will shape the design of future trials and will improve our understanding of diaphragm weakness in mechanically ventilated children in the ICU.

E.3.5 Procedures to minimize risk

All patients will be extensively monitored in the intensive care unit throughout the duration of the study. This will include close monitoring of cardio-respiratory parameters including heart rate, temperature, blood pressure, oxygen saturation, respiratory rate, and work of breathing. Intensive care unit physicians, nurses, and respiratory therapists will be present during the entire study, and will intervene as necessary should any treatment be indicated. In addition, to protect confidentiality of data, study forms will only be labeled with a unique number identifier, which can only be

linked to identifiable information only through a key with access restricted to the PI or research coordinator.

E4 Early Withdrawal of Subjects

The subject may be withdrawn from the study by the (1) study investigator or (2) the parent or legal guardian at any time after consent. The primary attending physician can also request that the principal investigator consider withdrawal of the patient from the study if they believe the study is no longer in the best interest of the patient.

E.4.1 When and How to Withdraw Subjects

Subjects can be withdrawn by the parents at any time, simply by requesting that the principal investigator withdraw the patient. The study investigator may withdraw the patient from the study if he or she believes that this is necessary to protect the health of the child, if the condition of the child changes such that continuation in the study poses additional risks, or if the child experiences an adverse event which changes the risk benefit profile of continuing in the study.

E.4.2 Data Collection and Follow-up for Withdrawn Subjects

If consent is withdrawn for participation in the research by the parent/guardian, then data collection will cease. Parents will be asked if we can keep existing data and follow clinical outcomes for intention to treat analysis. However, if they wish, existing data will be destroyed. If the study investigator withdraws the patient, then existing data will be preserved, and clinical outcome data detailed in section C.3.1. will continue to be collected to enable intention to treat analysis.

F Data Safety Monitoring Plan and Board

Please see separate Data Safety and Monitoring Plan and Data Safety and Monitoring Board Charter. An institutional DSMB has been created for this study.

The Data Safety Monitoring Plan details expected adverse events, with expected rates of occurrence.

G References

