Aim 1: The primary outcome is weaning duration. Sample size has been determined to adequately power 3 separate comparative analyses: (a) REDvent-acute versus Acute Phase control (b) REDvent-weaning phase versus Weaning Phase control (c) REDvent both phases versus control both phases. Power is based on 2 planned methods for analysis: cox proportional hazard ratios for multivariable analysis and univariate analysis with an independent t-test using log transformation (as needed) to account for the expected distribution of weaning duration. For all three of the planned comparisons above, with the proposed sample size we would be adequately powered (>0.8) to detect a difference in weaning duration of ≥ 1 day, or a hazard ratio of ≥ 1.4 between groups. The secondary outcomes are ventilator free days and extubation failure. Directly comparing control only patients to REDvent only patients, with an expected standard deviation for VFDs between 5 to 9 days, we will be able to detect a 2-day change in VFDs between groups with a power between 0.35 and 0.82. Re-intubation rates are expected to be 10%, allowing us to confirm that REDvent is not inferior to usual care in regards to re-intubation with a non-inferiority margin of 0.10 with a power of 0.8 and alpha of 0.05.

Aim 2: The primary outcome of this aim is weaning duration. For respiratory muscle strength we will compare the first measured aPiMax (after resolution of the acute phase, before the first SBT), the trajectory and value of the daily aPiMax during the weaning phase prior to extubation, the lowest and highest measured aPiMax, and aPiMax on the day of extubation against weaning duration. For analysis, aPiMax will be dichotomized at 30 cmH₂O, and weaning duration will be compared between patients with aPiMax > 30 versus ≤ 30 cmH₂O using a t-test with or without log-transformation, or Mann-Whitney U test, depending on the distribution. From our preliminary data, we anticipate at least 35% of patients (n=84) will have aPiMax ≤ 30 cmH₂O. Based on a similar power analysis as presented above, this would allow us to determine whether low aPiMax

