For all variables, descriptive statistics will be calculated, including means, standard deviations, medians, and interquartile ranges for continuous variables and frequency counts and percentages for categorical variables. Data will be examined for skewness, outliers, and systematic missing data. Transformations will be undertaken as needed. Comparisons of demographic and baseline variables will be obtained by treatment group.

D.6.4.1 SA 1 Analysis Plan: To determine if REDvent acute and/or weaning phase protocols can shorten the duration of weaning from MV (Primary outcome).

Primary analysis and sample size: The primary outcome for this aim is weaning duration. Because we seek to understand whether REDvent-acute and/or REDvent weaning have an independent effect on length of weaning, we propose a sample size to adequately power 3 separate comparative analyses: **(a)** REDvent-acute versus Acute Phase control **(b)** REDvent-weaning phase versus Weaning Phase control **(c)** REDvent both phases versus control both phases. We expect up to 12% mortality before the first SBT based on our Preliminary Data. These patients will not be included in the analysis for the primary outcome. From our pilot data (REDvent in both acute and weaning phases), the duration of the weaning phase in the intervention arm was 2.2 days, compared to 4 days in historical controls with a standard deviation of 2.1 days in the intervention arm and 2.8 days in the historical controls.

[figure not shown]

Figure 8: Power curve for a 1 day reduction in weaning

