Comparison (a) REDvent-acute versus control: A 1-day reduction in length of weaning is considered clinically significant (less sedative exposure, fewer nosocomial infections, lower healthcare costs). With a sample size of 276 patients (138 per arm), up to 12% mortality and 1% attrition or incorrect randomization, a minimum of 240 patients (120 per arm) will be available for analysis of the acute phase. Power is based on 2 planned methods for analysis: cox proportional hazard ratios for multivariable analysis and univariate analysis with an independent t-test using log transformation (as needed) to account for the expected distribution of weaning duration. For univariate analysis using the assumptions above, we would be able to detect a ≥ 1 -day reduction in weaning duration with an alpha of 0.05 and power of 0.9 (Figure 7). For the cox proportional hazard model, we would be able to detect a relative hazard ratio of 1.5 (ratio between control/intervention group) with a power of 0.9 or a hazard ratio of 1.4 with a power of 0.8.

Comparison (b) REDvent-weaning versus control: Patients who fail the initial SBT will undergo the weaning phase randomization. From our pilot data, approximately 25% of patients exposed to the intervention passed the initial SBT, corroborating previous studies.¹⁵ Thus, at least 180 patients (90 per arm) will receive weaning phase interventions. Using the same assumptions as above, we will be able to detect a ≥ 1 day

reduction in the length of the weaning phase (Figure 8), or a hazard ratio of 1.5 with an alpha of 0.05 and power of 0.8. Patients who do not pass the SBT by 28 days post the weaning phase randomization will be censored for analysis, as study interventions and daily monitoring will end on day 29.

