Comparison (c) REDvent versus control both phases: We will get an assessment of the cumulative effect of the intervention by comparing patients who received both REDvent-acute and REDvent weaning to patients who received only usual care in both phases. Because the rates of passage of the first SBT will differ between groups, there will not be an equal number of patients exposed to REDvent only as control only. Based on the assumptions above, we anticipate that of the 240 patients included in the analysis of weaning duration, 78 will be REDvent only, 72 will be control only, and 90 will be mixed. As such, the expected sample size comparing REDvent only to control only would allow us to detect a ≥ 1.1 - day reduction in weaning duration with a hazard ratio of 1.6 with a power of 0.8 and alpha of 0.05; or a ≥ 1.3 - day reduction in weaning duration with a hazard ratio of 1.6 with a power of 0.9.

All patients will be analyzed in the groups to which they were randomized for weaning duration, following intention to treat principles (allow for up to 1% incorrect allocation or attrition). Clinical variables (data collection table) will be tracked and compared between intervention and control groups for all 3 of the planned analyses (a-c). If there is an imbalance in any variable that may confound the relationship between weaning duration and REDvent, we will build a multivariable cox proportional hazard model to ensure that the measured treatment effect on weaning duration is retained after multivariable adjustment.

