retain an independent association with SBT failure. Because SBTs will be repeated daily, we will use a hierarchical logistic regression model to control for repeated measures from each patient as well as controlling for the other potential confounding variables detailed in the data collection table. We anticipate that 240 patients will undergo SBT testing, and 90% of these patients will pass the SBT within 28 days of the weaning phase randomization. As such, we would be able to include at least 20 variables in a multivariable hierarchical logistic regression model. Finally, we will determine whether common “phenotypes” for weaning failure can be determined. We anticipate four possible phenotypes by combining information from all available measures of capacity, load, effort, and architecture. Based on our preliminary data, we anticipate that patients with high load will be more likely to fail weaning, but that this effect will be more pronounced if they have diminished respiratory muscle capacity. We hypothesize that the rates of passage of the SBT will increase incrementally from phenotype 1 to 4: (1) Diminished capacity, high load and effort; (2) Normal capacity, high load and effort; (3) Diminished capacity, low load and effort; (4) Normal capacity, low load and effort. These phenotypes are exploratory; thus, no power analysis is provided.

D.6.4.3 SA3 Analysis Plan: To determine if patient effort of breathing during both acute and weaning phases of MV is independently associated with the development of respiratory muscle weakness.

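### The protocol summary claims power above 0.8 at HR 1.4 for all three comparisons, but the sample gives 0.62 and 0.54 for two of them; comparison (c) also lists one HR at two power levels

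*Combined protocol and SAP*

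**What the plan says.** The A2 Protocol Summary, Aim 1, makes one power statement for (a) REDvent-acute versus control, (b) REDvent-weaning versus control and (c) REDvent in both phases versus control in both: "For all three of the planned comparisons above, with the proposed sample size we would be adequately powered (>0.8) to detect a difference". The effect it names is a "difference in weaning duration of ≥ 1 day, or a hazard ratio of ≥ 1.4 between groups". The sentence is the same in the 300-patient and 276-patient versions of the protocol. Both versions plan for 240 evaluable patients.

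Section D.6.4.1 is more modest and treats each comparison separately:

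- (a), 120 per arm: "a hazard ratio of 1.4 with a power of 0.8", or HR 1.5 at 0.9.
- (b), 90 per arm: at least 1 day, "or a hazard ratio of 1.5 with an alpha of 0.05 and power of 0.8".
- (c), 78 versus 72: the sample would "allow us to detect a ≥ 1.1 - day reduction in weaning duration with a hazard ratio of 1.6" at power 0.8, and also "a ≥ 1.3 - day reduction in weaning duration with a hazard ratio of 1.6 with a power of 0.9".

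The Power analysis section of the Final SAP (July 2024) repeats the figures for (a) and (b), specifies two-sided alpha, and gives no hazard ratio for (c).

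**The concern.** The summary and the detailed section cannot both be right. At power 0.8 the detailed section needs a larger hazard ratio for (b) and (c) than the summary names, and for (c) a larger difference in days. Within (c), the difference in days rises from 1.1 to 1.3 as power goes from 0.8 to 0.9, as it should, but the hazard ratio printed beside it stays at 1.6.

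What is at stake is how a null or imprecise result for (b) or (c) is read. Someone relying on the summary would think that an HR of 1.4 had been excluded with better than 80% power, when the chance of detecting it was nearer 60% or 54%.

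**Working it through.** **Inputs.** Evaluable patients: 240 (120:120), 180 (90:90) and 150 (78:72), from D.6.4.1. Alpha: two-sided 0.05, from the Final SAP Power analysis. SDs: D.6.4.1 gives a "standard deviation of 2.1 days in the intervention arm and 2.8 days in the historical controls". Events: every evaluable patient is counted, which is the most favourable case.

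**Hazard-ratio formula (Schoenfeld).** Power = Φ(ln HR × √(D·p·(1−p)) − 1.96), where D is events and p the share in one arm. The detectable HR is exp((1.96 + z)/√(D·p·(1−p))), with z = 0.842 for power 0.8 and 1.282 for power 0.9. The square-root term is:

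- (a) √(240 × 0.25) = 7.746
- (b) √(180 × 0.25) = 6.708
- (c) √(150 × 0.52 × 0.48) = 6.119

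**Reproducing D.6.4.1 first.** HRs detectable at 0.8 are:

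- (a) exp(2.802/7.746) = 1.436
- (b) exp(2.802/6.708) = 1.518
- (c) exp(2.802/6.119) = 1.581

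Rounded to one decimal these are 1.4, 1.5 and 1.6, exactly as D.6.4.1 prints. For (a) at 0.9 the value is 1.52, printed as 1.5. These figures therefore stand, allowing for rounding.

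**The summary's HR 1.4** (ln 1.4 = 0.3365):

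- (a) 0.3365 × 7.746 − 1.96 = 0.646, power 0.74. The gap to 0.8 is the rounding of 1.44 to 1.4.
- (b) 0.3365 × 6.708 − 1.96 = 0.297, power 0.62.
- (c) 0.3365 × 6.119 − 1.96 = 0.099, power 0.54.

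HR 1.4 at power 0.8 needs about 278 events. Variants do not rescue (b) or (c):

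- Freedman's formula gives 0.61 and 0.53.
- One-sided 0.05 gives 0.73 and 0.66.
- Section D.6.4.2 expects that "90% of these patients will pass the SBT within 28 days of the weaning phase randomization". Taking 90% as events (162 and 135) gives 0.57 and 0.50.

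**The 1-day alternative.** SE = √(2.1²/n₁ + 2.8²/n₀), with power Φ(1/SE − 1.96).

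- (a) SE = √(12.25/120) = 0.320, power 0.88.
- (b) SE = √(12.25/90) = 0.369, power 0.77; the difference detectable at 0.8 is about 1.04 days, which rounds to 1 and is not disputed.
- (c) SE = √(4.41/78 + 7.84/72) = 0.407, power 0.69; detectable differences are 2.802 × 0.407 = 1.14 days at 0.8 and 3.242 × 0.407 = 1.32 days at 0.9.

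The two values for (c) match the printed 1.1 and 1.3, so D.6.4.1 used this scale, and 1 day falls short for (c).

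**HR 1.6 at two powers in (c)** (ln 1.6 = 0.470). 0.470 × 6.119 − 1.96 = 0.916, power 0.82. Power 0.9 needs exp(3.242/6.119) = 1.70 with 150 events, or about 190 events at HR 1.6.

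**The case against.** The strongest reply is that this is a stale line in a summary. The Final SAP does not carry the all-three claim, and D.6.4.1 gives a figure for each comparison, so anyone working from those sections is not misled. Cox stopped being the primary model in January 2023. The Final SAP also makes the four-group combination comparisons exploratory, although it still lists the combined comparison under the primary analysis. All of this stands and limits the importance of the point, but it does not make the sentence correct.

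A second reply is that the planned t-test may use a log transformation, so 0.69 for 1 day in (c) depends on the scale. That is fair. If durations are assumed lognormal, with log SDs of 0.63 to 0.80 derived from the pilot means and SDs, power for (c) is 0.58 to 0.79 for a fall from 4 to 3 days and 0.81 to 0.95 for a fall from 3.2 to 2.2. However, the protocol's own 1.1 and 1.3 days reproduce on the untransformed scale, and D.6.4.1 itself does not claim 1 day for (c).

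A reader might go further and infer that the January 2023 re-estimate of 230 patients was wrongly done as a Poisson calculation. With 230 × 0.87 = 200 evaluable and no overdispersion, a two-sided Wald calculation gives detectable reductions of 0.362 and 0.755 days, close to the stated 0.36 and 0.75. The documents do not establish the inference. They describe the calculation as negative binomial and record no dispersion, alpha or variance formula; other choices, such as one-sided alpha, leave room for some overdispersion. The Final SAP also rests its conclusions on the proportional odds model. At most, the inputs are unrecorded.

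**Conclusion.** The summary's claim fails for (b) and (c): power at HR 1.4 is 0.62 and 0.54, against a stated value above 0.8. These are best-case values at two-sided 0.05 with every patient an event, and the conflict with D.6.4.1 is visible without any calculation. The day alternative also falls short for (c), at 0.69 on the untransformed scale. The second HR of 1.6 in (c) is wrong as printed and should be about 1.70.

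Two stronger readings are not supported. Comparison (a) is not in error, since its 1.4 is 1.44 rounded. The January 2023 sample size is not shown to be wrong.

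No analysis is affected and data collection is complete, so this is a minor reporting correction.

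**What to change.** In the A2 Protocol Summary, replace the all-three sentence with the HR detectable at 80% power for each comparison: about 1.44 (a), 1.52 (b) and 1.58 (c), stating that every evaluable patient is assumed to have the event. Give at least 1.1 days for (c), as D.6.4.1 does. In D.6.4.1, comparison (c), restate the HR at 0.9 power as about 1.7.

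Optionally, record the dispersion and alpha used in January 2023 beside the 230-patient figure. Power should not be recalculated now that the data are complete.

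The cost is a few lines of wording. Some stated figures become less favourable. No patients, data or analyses change.

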Secondary Outcomes for SA 1: The 28 and 60 Day Ventilator Free Days (28D VFD, 60D VFD) will be secondary outcomes of this aim. Groups for VFD analysis will be based on any exposure to the intervention (acute or weaning) because some patients will never undergo a weaning phase randomization (i.e. died or were extubated right after the acute phase). If patients who died as well as those who dropped out are included in the VFD analysis, with the assumptions above regarding expected passing rate of SBTs, the estimated distribution of patients in 3 distinct groups will be: (a) REDvent only (n=108); (b) REDvent and control (n=90); (c) control only (n=102). We anticipate children in the REDvent only arm will have the most 28 D VFDs (anticipation 22), and those in the control only arm the least (anticipation 20). Directly comparing control only patients to REDvent only patients, with an expected standard deviation for VFDs between 5 to 9 days, we will be able to detect a 2-day change in VFDs between groups with a power between 0.35 and 0.82. Re-intubation rates are expected to be 10%, allowing us to confirm that REDvent is not inferior to usual care in regards to re-intubation with a non-inferiority margin of 0.10 with a power of 0.8 and alpha of 0.05. Finally, to ensure that REDvent is promoting greater patient effort of breathing and that the intervention does not alter clinical practice in the usual care arm, we will compare time weighted average values for direct measures of patient effort of breathing (PRP, PTP, Diaphragm Contractile Activity), and ventilator settings between intervention and control groups, and monitor the separation between groups over the time of the study.

D.6.4.2 SA2 Analysis Plan: To determine if changes to direct measures of respiratory muscle strength, load, effort, and architecture throughout the duration of MV are related to weaning outcomes.

Analysis and Sample Size: The primary outcome of this aim is weaning duration (as defined above). For this analysis, we will compare how each respiratory measure detailed in the data collection table relates to weaning duration. For respiratory muscle

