The primary analysis seeks to address if there are differences in length of weaning between: 1) REDvent-acute compared to usual care acute, 2) REDvent-weaning compared to usual care-weaning, and 3) REDvent-acute and weaning (combined) compared to usual care acute and weaning (combined). Analyses of these aims will follow the ITT principle. The primary analyses will compare median weaning duration between groups using a Mann-Whitney U test, or a t-test with transformation as necessary. The effect size (r) will also be computed to assess the magnitude of treatment effect. If imbalances in baseline characteristics are found between or across randomized treatment groups, a Cox proportional hazard model will be performed to adjust for covariates. The estimates (mean, median, or hazard ratio) and the associated 95% confidence interval, as well as the p-values, will be presented for interpretation.

Power analysis: For the primary outcome (weaning duration), a 1-day change in length of weaning is considered clinically significant. It is anticipated that up to 20% of patients may not achieve the primary outcome (successful passage of an SBT or extubation due to death or dropout); these patients will not be included in the primary outcome analysis but will be included in secondary outcomes. We are targeting an overall sample size of 300 patients, with a minimum of 240 patients (120 per arm) available for analysis of the primary outcome. Using the planned statistical tests above, this sample size would be able to detect a ≥ 1 -day change in weaning duration with a two-sided alpha of 0.05 and power of 0.9, or a relative hazard ratio of 1.5 (ratio between control/intervention group) with a power of 0.9 or a hazard ratio of 1.4 with a power of 0.8. Patients who fail the initial SBT will undergo the weaning phase randomization. From our pilot data, approximately 25% of patients exposed to the intervention passed the initial SBT. Anticipating 180 patients (90 per arm) will receive weaning phase interventions, there will be adequate power to detect a ≥ 1 day change in the length of the weaning phase, or a hazard ratio of 1.5 with an alpha of 0.05 and power of 0.8 in the weaning phase.

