Model assumptions and fit for multiple linear regression (with or without log transformation) will be assessed visually for normality of residuals as well as variance inflation factor and difference in betas (DFBETAS) for influential points. Model fit for binary multiple logistic regression will be assessed with Pearson Chi-square and deviance. Firth's penalized likelihood method will be used in subgroup analyses when event rates are small to reduce bias in the parameter estimates.⁴ When using negative binomial regression, model fit will be assessed for over and underdispersion with the scaled Pearson Chi-square/deviance and influential points assessed as previously described. The proportional hazards assumption will be assessed when using Cox proportional hazards modeling using graphical approaches ("log-log" figures and Kaplan-Meier curves) for each covariate. Repeated measures analysis for ventilator settings, lung mechanics, and respiratory measures will be assessed with linear mixed models and generalized linear mixed models that include a variable for time from randomization to control for correlation of values within each patient using the first-order autoregressive structure. The robust sandwich estimators for standard errors will be used to reduce heteroscedasticity when appropriate.

A detailed outline of each outcome's analysis approach to control for blocking variables and confounders is given in the Table 1. Pre-specified comparisons of interest are REDvent acute vs. usual care acute, REDvent weaning vs. usual care weaning, and four group combination: 1) REDvent acute + REDvent weaning 2) REDvent acute + usual care weaning 3) Usual care acute + usual care weaning 4) usual care acute + REDvent weaning. The four group combinations comparisons are exploratory and will only be considered if there are noted differences between both acute and weaning phase interventions.

October 2019- new milestone accrual plan

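### The protocol's exposure-based VFD groups put every early death in the two pure groups: contrasts with the mixed group are badly biased, the stated pure-group contrast modestly so, and the final SAP does not withdraw the rule

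*Combined protocol and SAP*

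**What the plan says.** **Final protocol (276 patients), D.6.4.1.** The paragraph on secondary outcomes for SA 1 sets the rule: "Groups for VFD analysis will be based on any exposure to the intervention (acute or weaning". It gives the reason: "because some patients will never undergo a weaning phase randomization (i.e. died or were extubated right after the acute phase". The expected sizes, with deaths and dropouts included, are "a) REDvent only (n=108); (b) REDvent and control (n=90); (c) control only (n=102". The paragraph then compares control-only directly with REDvent-only: anticipated means of 20 and 22 days, SD 5 to 9, and power 0.35 to 0.82 for a 2-day difference.

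Under comparison (c) of the same section, the 240 children expected in the weaning analysis divide differently: "78 will be REDvent only, 72 will be control only, and 90 will be mixed". Under comparison (b): "Patients who fail the initial SBT will undergo the weaning phase randomization". The pilot figure used there is that "approximately 25% of patients exposed to the intervention passed the initial SBT". Section C.3.1 scores death within the window as zero VFDs.

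**Final SAP (July 2024).** The primary-analysis paragraph lists acute, weaning and combined contrasts for length of weaning and adds: "Analyses of these aims will follow the ITT principle". Secondary outcomes, VFDs included, are to follow the same approach. Later: "Pre-specified comparisons of interest are REDvent acute vs. usual care acute, REDvent weaning vs. usual care weaning". The four-group combinations are exploratory and conditional on differences in both phases. The Table 1 row for 28-day VFDs has no exclusions, and the only change it records is the switch to a negative binomial model.

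**The concern.** Group membership under the protocol rule is settled after randomisation. A child assigned to control-acute who dies before an SBT stays in control-only for good. A child in the same arm who survives, fails the SBT and draws REDvent-weaning moves to the mixed group. The mixed group therefore has no deaths from before weaning randomisation, although later deaths can occur there. This is immortal-time bias, and because a death scores zero it acts directly on the endpoint.

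VFDs are a secondary outcome here, but the protocol names 28-day VFDs among the outcomes on which a Phase III trial would be powered. A difference created by the grouping could carry into that planning.

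**Working it through.** **1. Reproducing the group sizes.** The initial protocol has 300 children, 150 per arm. Losses of 13% + 7% = 20% are 60 children, 30 per arm, leaving 120 per arm. Let x and y be the first-SBT passers in REDvent-acute and control-acute, with failers split 1:1.

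- x + (120 − x)/2 = 78 gives x = 36 (30%).
- y + (120 − y)/2 = 72 gives y = 24 (20%).
- Mixed = 84/2 + 96/2 = 90.
- VFD groups: 78 + 30 = 108, 72 + 30 = 102, 90 + 0 = 90.

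The plan's sizes are reproduced exactly. Early losses are 30/150 = 20% of each randomised arm, but 30/108 = 27.8% of REDvent-only, 30/102 = 29.4% of control-only and 0% of mixed.

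**2. Reproducing the power.** Power = Φ(2 / [SD·√(1/n₁ + 1/n₂)] − 1.96). The two-sided 0.05 is an assumption, since none is stated for VFDs. With 108 and 102:

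- SD 5: 2/0.690 − 1.96 = 0.94, power 0.826.
- SD 9: 2/1.243 − 1.96 = −0.35, power 0.363.

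Both are close to the stated 0.82 and 0.35.

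**3. Size of the distortion at 276.** 276 − 240 = 36 lost, 18 per arm, so the groups become 96/90/90. Early deaths are 0.12 × 138 = 16.56 per arm. Assume 22 VFDs for every other child and no effect on VFDs.

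| Group | n | Early deaths | Mean VFDs |
|---|---|---|---|
| REDvent-only | 96 | 17.3% | 18.2 |
| Mixed | 90 | 0% | 22.0 |
| Control-only | 90 | 18.4% | 18.0 |
| Any REDvent, pooled | 186 | 8.9% | 20.0 |
| Either acute arm | 138 | 12.0% | 19.4 |

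Spurious differences from control-only:

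- Mixed: 0.184 × 22 = 4.0 days.
- Pooled: (0.184 − 0.089) × 22 = 2.1 days.
- REDvent-only: 16.56 × (1/90 − 1/96) × 22 = 0.25 day.

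The acute-arm difference is 0. At 20 VFDs per survivor each figure is multiplied by 20/22 (3.7, 1.9 and 0.23).

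**4. Sensitivity to first-SBT passage.** With 25% passing in both arms, each pure group is 18 + 30 + 45 = 93. Mixed then exceeds control-only by 22 × 16.56/93 = 3.9 days, pooled exceeds it by 22 × (16.56/93 − 16.56/183) = 1.9 days, and the pure groups do not differ.

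Suppose also that passers have d more VFDs than failers (assumption), with the survivors' mean held at 22 and the 1.44 dropouts per arm given the failers' value.

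- d = 4 (25 v 21): control-only is (30×25 + 46.44×21)/93 = 18.55. Mixed exceeds it by 2.4 days and pooled (19.76) by 1.2.
- d = 3 (24.25 v 21.25): control-only is 18.43. The excesses are 2.8 and 1.4 days.

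**5. Range for the stated contrast (108 v 102, 30% v 20% passing).**

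- 13% scored zero: 19.5 × (1/102 − 1/108) × 22 = 0.23 day.
- All 20% scored zero: 30 × (1/102 − 1/108) × 22 = 0.36 day.
- Passers 24 and failers 20: the acute-arm difference is 12 × 4/150 = 0.32, but the pure groups show 17.72 − 17.12 = 0.60 (13% at zero) to 15.78 − 15.06 = 0.72 (20% at zero), an excess of 0.28 to 0.40.

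In 4,000 simulated trials (150 per arm, 13% deaths, SD 5), type I error of the pure contrast was 5.4% with equal pass rates. At 30% v 20% the mean difference was 0.31 day.

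**6. What restores the comparison.** Giving weight 2 to the failers kept in each pure group yields 36 + 2×42 + 30 = 150 and 24 + 2×48 + 30 = 150. Early losses are again 20% on each side. In the simulation this reduced 0.31 day to 0.03, equal to the acute-arm difference in the same runs.

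**7. Power at 276, 2-day difference, SD 9 to 5.** Exposure groups, 96 v 90: 0.33 to 0.78. Acute arms, 138 v 138: 0.45 to 0.91.

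**The case against.** The strongest reply has two parts.

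First, the contrast that the protocol powers is pure against pure. Moving survivors into the mixed group depletes both pure groups almost equally, so most of the distortion cancels. That stands. A reader might take the any-exposure wording to mean that all REDvent-exposed children are pooled against control-only, and conclude that the 2-day target could arise from the grouping alone. The documents do not support this: they define three separate groups, attach the means and power to the two pure ones, and nowhere state a pooled test. A reader might also infer an as-treated analysis that moves non-adherent children between groups. The counts follow the assigned phases, and no text moves anyone for non-adherence.

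Second, the final SAP is the later and fuller document. Its own timeline calls the protocol's plan basic. It points to the randomised contrasts, excludes nobody from the VFD analysis and makes the four-group comparisons exploratory. This also stands, and an acute-arm VFD analysis under it is free of the problem. Three gaps remain. The exposure rule is never withdrawn. The protocol's intention-to-treat sentence is confined to weaning duration, and the SAP's is attached to the length-of-weaning comparisons. The SAP's combined comparison does not say where children who were never weaning-randomised belong.

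**Conclusion.** The exposure rule is unsound as the protocol states it, but the damage depends on the contrast. Comparisons with the mixed group, or with a pooled any-REDvent group if anyone formed one, are heavily biased: about 4 and 2 days at 276 patients, falling to about 2.4 and 1.2 days if first-SBT passers have 4 more VFDs than failers. The stated REDvent-only against control-only contrast is biased by about 0.2 to 0.4 day towards REDvent, and only because the plan's counts imply first-SBT pass rates of 30% v 20%. It would be wrong to conclude that the randomised VFD comparison is broken throughout.

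These sizes rest on the plan's mortality and pass rates and on assumed VFDs per survivor, since the plan gives group means only. Two current texts allow different VFD analyses of the same data, and the protocol's VFD group sizes still sum to 300.

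**What to change.** - State in both protocol and SAP that 28- and 60-day VFDs are compared in all randomised patients by acute-phase arm (138 v 138), and separately by weaning-phase arm among children who were re-randomised.
- Withdraw the exposure-based grouping as the VFD comparison.
- If a both-phases VFD comparison is kept, label it exploratory and weight first-SBT failers by 2 so that children never weaning-randomised are correctly represented. Tie the weight to actual re-randomisation: D.3.5 lets the team extubate a child who has failed the SBT, and such a child keeps weight 1.
- Restate sizes and power for 276. The exposure groups are about 96/90/90 with power 0.33 to 0.78, not 108/90/102 with 0.35 to 0.82. The acute-arm contrast has power 0.45 to 0.91 for 2 days.

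The cost is wording in two documents. The acute-arm effect is diluted because weaning assignment is mixed within each arm, so the true difference may be below 2 days and the power lower than shown. The weighted comparison keeps the cumulative question available.
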